9. ADVERSE EVENTS REPORTING

9.1. DEFINITIONS

9.1.1. Adverse Event

An adverse event (AE) is any untoward medical occurrence in a patient or a clinical investigation patient administered a pharmaceutical product which does not necessarily have a causal relationship with this treatment.

An AE can therefore be any unfavorable and unintended sign (e.g., an abnormal laboratory finding), or a disease temporally associated with the use of a medicinal product, whether or not considered related to the medicinal product.

Any event involving adverse drug reactions, illnesses with onset during the study or exacerbations of pre-existing illnesses should be recorded, including but not limited to clinically significant changes in physical examination findings and abnormal objective test findings (e.g., x-Ray, ECG). The criteria for determining whether an abnormal objective test finding should be reported as an AE are as follows:

- the test result is associated with clinically significant symptoms, and/or
- the test result leads to a change in the study dosing or discontinuation from the clinical trial, significant additional concomitant drug treatment or other therapy, and/or
- the test result leads to any of the outcomes included in the definition of a SAE, and/or
- the test result is considered to be an AE by the Investigator.

9.1.2. Serious Adverse Event (SAE)

A Serious Adverse Event (SAE) is any adverse experience occurring at any dose that:

- results in death (is fatal),
- is life-threatening,
- requires or prolongs inpatient hospitalization,
- results in persistent or significant disability or incapacity,
- is a congenital anomaly or birth defect,
- is medically significant, or
- is any suspected transmission of an infectious agent via a medicinal product.

Medical and scientific judgment should be exercised in deciding whether expedited reporting is appropriate in other situations such as an important medical event that may not be immediately life-threatening or result in hospitalization but may jeopardize the patient or may require intervention to prevent one of the outcomes listed in the above definition.

9.1.2.1. Death

Death as such is the outcome of a SAE and should not be used as the SAE term itself. Instead, the cause of death should be recorded as the SAE term.

9.1.2.2. Life-Threatening Event

Any event in which the patient was at risk of death at the time of the event; it does not refer to an event which hypothetically might have caused death if it were more severe.

9.1.2.3. Hospitalization or Prolongation of Hospitalization

Any AE requiring hospitalization (or prolongation of hospitalization) that occurs or worsens during the course of a patient's participation in a clinical trial must be reported as a SAE unless exempted from SAE reporting (see Section [9.2.2](#)). Prolongation of hospitalization is defined as any extension of an inpatient hospitalization beyond the stay anticipated/required for the initial admission, as determined by the Investigator or by the treating physician.

Hospitalizations that do not meet criteria for SAE reporting are:

- a. Reasons described in protocol [e.g., investigational medicinal product (IMP) administration, protocol-required intervention/investigations, etc.]. However, events requiring hospitalizations or prolongation of hospitalization as a result of a complication of therapy administration or clinical trial procedures will be reported as SAEs.
- b. Hospitalization or prolonged hospitalization for technical, practical or social reasons, in absence of an AE.
- c. Pre-planned hospitalizations: any pre-planned surgery or procedure must be documented in the source documentation. Only if the pre-planned surgery needs to be performed earlier due to a worsening of the condition, should this event (worsened condition) be reported as a SAE.

Other situations that MUST NOT be considered as hospitalizations are the following:

- d. An emergency visit due to an accident where the patient is treated and discharged.
- e. When the patient is held 24 hours for observation and finally is not admitted.
- f. Planned treatments at sites not associated to a hospital and generally considered as minor surgical procedures (i.e., laser eye surgery, arthroscopy, etc).

9.1.3. Unlisted/Unexpected Adverse Event

An AE, the nature or severity of which is not consistent with the applicable reference safety information.

The Sponsor will use as the reference safety information for the evaluation of listedness/expectedness the following documents:

- The current investigator brochure (IB) for any study drug/IMPs without a marketing authorization or used outside the conditions of its marketing authorization.
- The summary of product characteristics (SPC) or its national equivalent [i.e., U.S. package inserts (USPI)] defined in the protocol for non-Pharma Mar IMPs used within the conditions of its marketing authorization.

9.1.4. Adverse Events Related to Study Drug/s (IMP)

An AE is considered related to a study drug/IMP if the Investigator's assessment of causal relationship to the IMP is "1-Yes".

The Investigator will assess the causal relationship of each of the IMPs to the SAE.

The Sponsor may also consider related to the study drug/IMP those events for which the Investigator assesses the causal relationship with the IMP as "Unk" when it cannot rule out a role of the IMP in the event. See below (Section [9.1.6](#)) for causality scale.

9.1.5. Expedited Reporting

The Sponsor is responsible for the appropriate expedited reporting of SAEs to the Regulatory Authorities. The Sponsor will also report all SAEs that are unlisted and related to the study drug/s (IMP/s), to the Investigators and to the Independent Ethics Committees/Institutional Review Board (IECs/IRBs) according to the current legislation unless otherwise required and documented by the IECs/IRB.

9.1.6. Assessment of Causal Relationship to the Study Drug/IMP

The Investigator must provide an assessment of causal relationship of each of the clinical trial IMPs (including combination and comparator products) to each SAE according to the following scale:

- | | |
|----------|--|
| Y | There is a reasonable possibility that the IMP/s caused the SAE. |
| N | There is no reasonable possibility that the IMP/s caused the SAE and other causes are more probable. |

Unk. Only to be used in special situations where the Investigator has insufficient information (i.e., the patient was not seen at his/her centre) if none of the above can be used.

9.2. PROCEDURES

9.2.1. Reporting Adverse Events

The Sponsor will collect AEs until 30 days after administration of the last dose of study drug/IMP. All AEs suspected to be related to the study drug/IMP must be followed after the time of therapy discontinuation until the event or its sequelae resolve or stabilize at an acceptable level to the Investigator and the Sponsor.

All AEs must be recorded using medical terminology in the source document and the CRF. Whenever possible, the Investigator will record the main diagnosis instead of the signs and symptoms normally included in the diagnoses.

Investigators must assess severity (grade) of the event following the NCI-CTCAE v. 3.0 and assign relationship to each study drug/IMP; pursue and obtain information adequate both to determine the outcome and to assess whether it meets the criteria for classification as a SAE requiring immediate notification to PharmaMar or its designated representative. The Investigator must provide any relevant information as requested by the Sponsor in addition to that on the CRF.

Abnormal laboratory tests occurring during the study are AEs, but they should be collected only in the AE section of the CRF in some cases (please refer to the CRF guidelines for comprehensive information).

9.2.2. Reporting Serious Adverse Events

The Sponsor will collect SAEs from the signing of the Informed Consent Form. If the patient is definitively included in the study, this information will also be recorded in the AE section of the CRF.

SAEs will be collected until 30 days after administration of the last dose of study drug/IMP. Beyond this period of time, only those SAEs suspected to be related need to be reported. Nonetheless, the Sponsor will evaluate any safety information that is spontaneously reported by an Investigator beyond the time frame specified in the protocol.

All SAEs (as defined above) regardless of treatment group or relationship to the study drug/IMP must be reported within 24 hours to the Pharma Mar Pharmacovigilance function by fax ([contact]) or telephone ([contact]). Out of office hours (GMT), assistance on SAE reporting can be obtained by calling the Pharmacovigilance Service at [contact].

The preferred reporting method is by faxing the completed SAE form. An initial report by telephone must be followed by a completed "Serious Adverse Event Form" from the investigational staff within one working day.

All SAEs suspected to be related to the IMP/s must be followed until the event or its sequelae resolves or stabilizes at an acceptable level by the Investigator and the clinical monitor or his/her designated representative.

Death as such, is the outcome of a SAE and should not be used as the SAE term itself. Instead the cause of death should be recorded as the SAE term. When available, the autopsy report will be provided to the Sponsor.

9.2.3. Reporting Pregnancy Cases Occurred within the Clinical Trial

National regulations require that clinical trial Sponsors collect information on pregnancies occurring during clinical trials, in which exposure to the IMPs at any time during pregnancy, via either maternal or paternal exposure, is suspected.

Therefore, pregnancy and suspected pregnancy (including a positive pregnancy test regardless of age or disease state) of a female patient or the female partner of a male patient occurring while the patient is on study drug, or within 30 days of the patient's discontinuation visit, are considered immediately reportable events.

The Investigator will report the following events immediately and always within 24 hours from first knowledge:

- Any occurrence of a pregnancy where any kind of exposure to the IMP/s is suspected.
- Possible exposure of a pregnant woman (this could involve a partner of a male patient or a pregnant female who came in contact with the clinical trial IMP/s).
- All reports of elevated/ questionable or indeterminate beta human chorionic gonadotrophins (β hCGs).

Immediately after detecting a case of suspected pregnancy in a female clinical trial patient, the decision on her continued participation in the clinical trial will be jointly taken by the trial patient, the Investigator and the Sponsor, with the patient's best interest in mind. A decision to continue the pregnancy will require immediate withdrawal from the trial. If the trial is blinded, the Investigator will open the blind whenever the treatment information is needed for the management of the patient.

Any pregnancy, suspected pregnancy, or positive pregnancy test must be reported to PharmaMar Pharmacovigilance immediately by facsimile using the Pregnancy Report form. In the case of pregnancy of the female partner of a trial Patient the Investigator will obtain her informed consent to provide the information by using the applicable form provided by the Sponsor who will also advise the Investigator in these situations.

The Investigator will follow the pregnancy until its outcome, and must notify PharmaMar Pharmacovigilance the outcome of the pregnancy within 24 hours of first knowledge as a follow-up to the initial report.

For any event during the pregnancy, which meets a seriousness criterion (including fetal or neonatal death or congenital anomaly), the Investigator will also follow the procedures for reporting SAEs (complete and send the SAE form to PharmaMar Pharmacovigilance by facsimile within 24 hours of the Investigator's knowledge of the event).

All neonatal deaths that occur within 30 days of birth should be reported, without regard to causality, as SAEs. In addition, any infant death at any time thereafter that the Investigator suspects is related to the exposure to the study drug/IMP should also

be reported to PharmaMar Pharmacovigilance by facsimile within 24 hours of the Investigators' knowledge of the event.

10. STATISTICAL METHODS

The statistical analysis will be done by the Sponsor or under the Sponsor's authority.

10.1. SAMPLE SIZE

In this phase II trial, efficacy of PM00104 will be evaluated in two different groups of patients with endometrial or cervical cancer. A total of 62 evaluable patients are expected to participate in this clinical trial:

- 30 patients in Group 1 (endometrial cancer), and
- 32 patients in Group 2 (cervical cancer).

A different ORR is to be expected depending on the type of cancer. Thus, patients with endometrial cancer may achieve higher response rates with second-line single-agent therapies (around 25-30%) (6) than patients with cervical cancer (around 15-20%) (79, 80). Therefore, the sample size has been calculated in each group using a similar design (based on the Simon two-stage design for phase II trials) (81), but using different figures for null and alternative hypotheses.

Group 1 (endometrial cancer): patients with endometrial cancer who have received one previous systemic chemotherapy line for advanced/metastatic disease (excluding chemosensitizing chemotherapy); prior hormone therapy and biological therapy are allowed.

A Simon two-stage design will be adopted in this group to test the null hypothesis that the ORR by RECIST is $\leq 10\%$ *versus* the alternative that $\text{ORR} \geq 30\%$ (two-sided test; $\alpha=0.1$ and $\beta=0.1$). A maximum of 30 evaluable patients will be included in this group. In a first stage, 10 evaluable patients will be recruited. If one or more (≥ 1) patients achieve an objective response, the accrual in this group will be expanded with 20 additional evaluable patients. If the total number of patients with objective response is 6 or more (≥ 6) in 30 evaluable patients (i.e., an ORR in the whole study of at least 20%), the null hypothesis will be rejected and PM00104 will be considered for further clinical development in endometrial cancer.

Group 2 (cervical cancer): patients with cervical cancer who have received one previous systemic chemotherapy line for advanced/metastatic disease (excluding chemosensitizing chemotherapy); prior hormone therapy and biological therapy are allowed.

A Simon two-stage design will be adopted in this group to test the null hypothesis that the ORR by RECIST is $\leq 5\%$ *versus* the alternative that $\text{ORR} \geq 20\%$ (two-sided test; $\alpha=0.1$ and $\beta=0.1$). A maximum of 32 evaluable patients will be included in this group. In a first stage, 18 evaluable patients will be recruited. If one or more (≥ 1) patients achieve an objective response, the accrual in this group will be expanded with 14 additional evaluable patients. If the total number of patients with objective response is 4 or more (≥ 4) in 32 evaluable patients (i.e., an ORR in the whole study of at least 12.5%), the null hypothesis will be rejected and PM00104 will be considered for further clinical development in cervical cancer.

Early stopping rule

An early stopping rule for excessive toxicity will be evaluated when ten patients in each group will be recruited and followed for at least four weeks. A "serious toxicity" rate (STR) of 40% or more will be considered inadequate. The following are considered serious toxicities:

- Drug-related grade 4 neutropenia lasting for more than seven days.
- Grade 4 thrombocytopenia.
- Grade 3/4 nausea/vomiting despite adequate prophylaxis.
- Grade 3/4 transaminase increase lasting for more than seven days.
- Grade 3/4 fatigue.
- Any other grade 3/4 drug-related event leading to early study discontinuation.

If ≥ 4 patients of the first 10 patients had one of these serious toxicities, the trial will be stopped and the recommended dose and/or administration schedule for phase II will be re-evaluated.

With this stopping rule, the probability of $\geq 4/10$ STR in the sample (if the true probability of STR is $< 1/6$) is 0.0697. On the other hand, the probability of observing $\leq 3/10$ STR in the sample (if the true probability of STR is $> 40\%$) would be 0.3822.

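### Both Simon designs are labelled two-sided at alpha 0.1, but the hypotheses and go rules are one-sided; the label should read one-sided alpha 0.10 (attained 0.069 and 0.072)

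*Protocol*

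**What the plan says.** Protocol section 10.1 (Sample Size) adopts a Simon two-stage design in each group and labels each one "two-sided test; $\alpha=0.1$ and $\beta=0.1". The label appears six times: for each group in the protocol synopsis (Sample Size Considerations), for each group in protocol 10.1, and for each group in SAP 6.1.

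The design that follows the label is the same in all three sections:

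- **Group 1 (endometrial).** The null is a response rate of at most 10% and the alternative is at least 30%. On the first stage: "In a first stage, 10 evaluable patients will be recruited". With at least one response, "the accrual in this group will be expanded with 20 additional evaluable patients". The null is then rejected under this rule: "If the total number of patients with objective response is 6 or more (≥ 6) in 30 evaluable patients".
- **Group 2 (cervical).** The null is at most 5% and the alternative is at least 20%. The first stage has 18 patients. With at least one response, 14 more are added, making 32. The null is rejected under this rule: "If the total number of patients with objective response is 4 or more".

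Neither document gives a rule that rejects the null for a low count. Zero responses in the first stage means only that accrual is not expanded.

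**The concern.** A two-sided test can reject in either direction. Here the null already contains every low response rate, so a low count cannot be evidence against it, and the only rejection region is at the top. The label contradicts the hypotheses and the decision rule printed beside it.

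What is at stake is how the false-go risk is understood, meaning the chance of recommending further development when the true rate is only 10% or 5%. By convention a two-sided 0.10 test puts 0.05 in each tail. A reader who applies that convention would believe that the false-go risk in each group is held to 5%.

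**Working it through.** **Inputs** (protocol 10.1, repeated in the synopsis and SAP 6.1)

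| | Group 1 | Group 2 |
|---|---|---|
| Null rate p0 | 0.10 | 0.05 |
| Alternative rate p1 | 0.30 | 0.20 |
| First stage n1 | 10 | 18 |
| Second stage n2 | 20 | 14 |
| Continue if | at least 1 response | at least 1 response |
| Reject the null if total is at least c | 6 | 4 |

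**Formula.** With X1 and X2 the responses in the two stages, both binomial with rate p:

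P(reject | p) = sum over x1 ≥ 1 of P(X1 = x1 | n1, p) × P(X2 ≥ c − x1 | n2, p)

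At p0 this is the type I error, all of it in the upper tail. At p1 it is the power. Products below come from unrounded values.

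**Step 1. Type I error, Group 1 (p = 0.10)**

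- x1 = 1: 0.38742 × 0.04317 = 0.01673
- x1 = 2: 0.19371 × 0.13295 = 0.02575
- x1 = 3: 0.05740 × 0.32307 = 0.01854
- x1 = 4: 0.01116 × 0.60825 = 0.00679
- x1 = 5: 0.00149 × 0.87842 = 0.00131
- x1 ≥ 6: 0.00015 × 1 = 0.00015

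Total **0.0693**.

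**Step 2. Type I error, Group 2 (p = 0.05)**

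- x1 = 1: 0.37631 × 0.03005 = 0.01131
- x1 = 2: 0.16835 × 0.15299 = 0.02575
- x1 = 3: 0.04726 × 0.51233 = 0.02421
- x1 ≥ 4: 0.01087 × 1 = 0.01087

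Total **0.0721**.

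**Step 3. Power**

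- Group 1 at 0.30: 0.09231 + 0.20847 + 0.25736 + 0.19859 + 0.10284 + 0.04735 = **0.907**
- Group 2 at 0.20: 0.0447 + 0.1382 + 0.2196 + 0.4990 = **0.901** (unrounded 0.90147)

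Both designs therefore reproduce the plan's stated limits, alpha 0.10 and beta 0.10, when alpha is read as one-sided. A cut-off one response lower would break the limit: the type I error is 0.160 at 5 or more of 30, and 0.202 at 3 or more of 32.

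**Step 4. Two-sided 0.10, equal tails.** The upper tail may hold at most 0.10 / 2 = 0.05. The attained values of 0.0693 and 0.0721 both exceed it.

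**Step 5. Two-sided 0.10, outcomes ordered by null probability.** A two-sided exact test can instead sum the null probabilities of all outcomes no more likely than the one observed.

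- Group 1: stopping with 0 of 10 has probability 0.9^10 = 0.349. A final total of 1 has 0.0471, a total of 5 has 0.0912, and a total of 6 has 0.0443. Only totals of 6 or more are as unlikely as 6, so its p-value is 0.0693. At 5 the p-value is 0.0912 + 0.0471 + 0.0693 = 0.208. At a total of 1 it is 0.0471 + 0.0693 = 0.116, so the null is not rejected there.
- Group 2: stopping with 0 of 18 has probability 0.95^18 = 0.397. The p-value at 4 is 0.0721. At 3 it is 0.1298 + 0.0721 = 0.202.

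Under this ordering the lower rejection region is empty, and the 0.10 cut-offs are exactly the printed ones.

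**The case against.** The strongest defence is Step 5. The printed cut-offs also arise from a recognised two-sided exact test at 0.10, because the low outcomes are too probable under the null to be rejected. On that reading no figure in the plan is wrong, total type I error is below 0.10, and the conflict comes from an equal-tails convention that the documents never state. The go rule is also an explicit count whose direction is plain in the same paragraph. The SAP response tables report counts with 95% intervals, and SAP 7.4 treats any tests as exploratory at 5%.

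Most of this stands. It shows that this is not an arithmetic error and that the practical effect is small. It also rules out two stronger readings that a reader might infer:

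- **That 30 and 32 patients cannot have come from any two-sided 0.10 test.** Step 5 shows that they can. The numerical conflict depends on the equal-tailed convention.
- **That the trial is undersized or its cut-offs too low.** The designs meet alpha 0.10 and beta 0.10 as upper-tail limits, and nothing in the documents commits the sponsor to 0.05 in the upper tail.

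The defence does not rescue the label. The documents mention no ordering by probability. They state a composite null of the at-most form, an upper alternative, and rejection for high counts only. That is a one-sided test, whichever two-sided procedure happens to share its cut-offs.

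**Conclusion.** The label is wrong as written. It is an inconsistency in a stated property of the primary test, and its severity is minor. The contradiction with the hypotheses and the rejection rules can be read directly from the text. The numerical gap, 6.9% and 7.2% against 5%, applies only to a reader who assumes equal tails. A reader who takes 0.1 as the ceiling on a false go is protected, because both attained values lie below it.

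The attained figures assume independent binomial responses, exactly 30 and 32 evaluable patients, and stage rules followed as printed. No patient, cut-off or go decision is affected.

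**What to change.** At all six places (the synopsis, protocol 10.1 and SAP 6.1, each for both groups) replace the label with:

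- Group 1: one-sided alpha = 0.10, beta = 0.10; attained alpha 0.069, power 0.907.
- Group 2: one-sided alpha = 0.10, beta = 0.10; attained alpha 0.072, power 0.901.

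Changing the sidedness is the necessary correction. Adding the attained values lets a reader see the false-go risk without recomputing it. The cost is wording only. Leave cut-offs, stage sizes, sample sizes and go decisions unchanged.

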PM104-A-004-05§ (1-hour Day 1, 8 and 15 q4wk)	2 (Europe)	49	2.0	1.5	
 Dose level 7 (2 mg/m², RD): grade 4 lipase increase. Dose level 8 and 9 (2.5 and 3.0 mg/m², MTD): grade 3/4 asthenia, grade 3 nausea, grade 1 neutropenia and thrombocytopenia leading to two missing infusions, grade 3 febrile neutropenia, grade 3 anemia, grade 4 neutropenia, grade 4 thrombocytopenia and grade 4 leukopenia. 	Closed (65)

* Additionally, grade 4 troponin I increase without cardiac symptoms or ECG alterations was also reported (no DLT).

**The highest dose level reached up to December 2008 was 3.5 mg/m² (three patients enrolled).

***Recommended dose not achieved; dose intensity is expected to be 1.3 mg/m²/week.

****Prematurely closed due to low recruitment and unpractical dosing schedule.

†The highest dose level reached was 0.475 mg/m²/day.

§This schedule is the same than that used in the current phase II study: PM104-B-001-09.

In all studies, escalating dose cohorts are 1 to 3-6 patients per dose level. DLT, dose-limiting toxicities; ECG, electrocardiogram; MTD, maximum tolerated dose; RD, recommended dose; q3wk, every 3 weeks; q4wk, every 4 weeks

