7.2.2. Criteria for Treatment Continuation

In order to be re-treated on Day 1 of a new cycle, the patients will have to fulfill the same criteria as at study entry ([Table 11](#)).

If these criteria are not met on Day 1 of a new cycle, treatment administration should be delayed up to two weeks and reevaluated weekly. The new cycle will start upon recovery of these parameters, according to these same criteria.

A maximum delay of two weeks is allowed for recovery from drug-related AEs. If toxicities have not recovered after a maximum delay of two weeks, the patient should discontinue the treatment. In the event of obvious clinical benefit, the patient will remain on treatment only after having discussed and agreed upon the case with the Sponsor, and upon recovery of all parameters according to the aforementioned criteria.

In order to be re-treated on Day 8 and Day 15 of each cycle, the patients will have to fulfill the criteria also described in [Table 11](#). If these criteria are not met on Day 8 or Day 15, the respective infusion will be skipped. If both Day 8 and Day 15 infusions cannot be administered for any reason, the patient should discontinue the treatment, except in the event of obvious clinical benefit, in which case the patient will be allowed to remain on treatment only after having discussed and agreed upon the case with the Sponsor, and upon subsequent recovery of all parameters according to the aforementioned criteria.

Table 11. Criteria for continuation of treatment.

Parameter	Value on Day 1	Value on Day 8/15
Platelet count	$\geq 100 \times 10^9/l$	$\geq 75 \times 10^9/l$
Hb	≥ 9 g/dl	≥ 9 g/dl
ANC	$\geq 1.5 \times 10^9/l$	$\geq 1.0 \times 10^9/l$
AP	$\leq 2.5 \times$ ULN ($\leq 5 \times$ ULN if bone metastases)	$\leq 2.5 \times$ ULN ($\leq 5 \times$ ULN if bone metastases)
ALT, AST	$\leq 2.5 \times$ ULN ($\leq 5 \times$ ULN if hepatic metastases)	$\leq 2.5 \times$ ULN ($\leq 5 \times$ ULN if hepatic metastases)
Total bilirubin	$\leq 1.5 \times$ ULN*	$\leq 1.5 \times$ ULN*
Calculated creatinine clearance (using Cockcroft and Gault formula)	≥ 30 ml/min**	≥ 30 ml/min**
Other non-hematological related events, including renal function (except alopecia and/or vomiting in patients not receiving optimal antiemetic prophylaxis).	NCI-CTCAE grade ≤ 1 (\leq grade 2 in case of asthenia).	NCI-CTCAE grade ≤ 1 (\leq grade 2 in case of asthenia).

[figure not shown]
*Unless due to Gilbert's syndrome.

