7.2.3.1. Hematological Toxicity

The PM00104 dose administered to the patients will be reduced based on the nadir value of the platelet count and the ANC measured in the preceding cycle. In the event of a platelet count < 25 x 10⁹/l or an ANC < 0.5 x 10⁹/l lasting ≥ 5 days or associated with fever, sepsis or infection in the preceding cycle, the dose administered to the patient in following cycles will have to be reduced by one level ([Table 13](#)). In addition, re-treatment on the next infusion will only be allowed if the patient fulfils all pertinent criteria (see Section [7.2.2](#)).

Table 13. Dose adjustments due to hematological toxicity.

Toxicity	PM00104 dose
Grade 4 neutropenia (ANC < 0.5 x 10 ⁹ /l) lasting ≥ 5 days. Grade 4 neutropenia with fever (≥38.5°C). Grade 4 neutropenia with sepsis or severe infection.	Decrease one dose level
Thrombocytopenia. Platelets < 25 x 10 ⁹ /l	Decrease one dose level

Any dose reductions due to treatment-related hematological toxicities other than those listed in [Table 13](#) will have to be discussed and agreed with the Sponsor.

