7.2.3.2. Non-hematological Toxicity

In the event of non-hematological toxicity, the PM00104 dose administered to the patients will have to be reduced in case of:

- Any other grade 3/4 drug-related non-hematological AE, excluding alopecia, nausea/vomiting not treated with prophylactic medication or hypersensitivity reactions (patients with grade 3/4 hypersensitivity reactions should be discontinued from the study; see Section [5.2.1.2](#)).

- Any increase in cardiac troponin I ≥ 0.1 ng/ml, together with evidence of cardiac damage by ECG or ECHO.
- Decrease in the LVEF $>20\%$ from the patient baseline value and $<50\%$.

Any dose reductions due to treatment-related non-hematological toxicities other than those listed above will have to be discussed and agreed with the Sponsor.

Following the resolution of any of the aforementioned hematological or non-hematological toxicities, patients may continue treatment at one dose level below. If drug-related toxicities reappeared in the following drug administrations, a second dose reduction to a level below is allowed. If more than two dose reductions are required, the toxicity will be considered unacceptable and the patient must be withdrawn from the study. Exceptionally, patients recovering from the toxicity might continue treatment if there is objective evidence of antitumor response. This must always be discussed with the Sponsor.

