6.2 Interim analyses

Interim efficacy analysis will be performed when the 10 first evaluable patients have been recruited in the group 1 and 18 patients have been recruited in the group 2. In addition, a safety evaluation will be performed when 10 patients in each group will be recruited and followed for at least four weeks. The study will be stopped, and the recommended dose re-evaluated if the stopping rule described below is met in any of the groups.

Other non-scheduled interim analyses might be performed exclusively for enhancing the safety of the patients.

Early stopping rule:

An early stopping rule for excessive toxicity will be evaluated when ten patients in each group will be recruited and followed for at least four weeks. A "serious toxicity" rate (STR) of 40% or more will be considered inadequate. The following are considered serious toxicities:

- Drug-related grade 4 neutropenia lasting for more than seven days.
- Grade 4 thrombocytopenia.
- Grade 3/4 nausea/vomiting despite adequate prophylaxis.
- Grade 3/4 transaminase increase lasting for more than seven days.
- Grade 3/4 fatigue.
- Any other grade 3/4 drug-related event leading to early study discontinuation.

If ≥ 4 patients of the first 10 patients had one of these serious toxicities, the trial will be stopped and the recommended dose and/or administration schedule for phase II will be re-evaluated.

With this stopping rule, the probability of $\geq 4/10$ STR in the sample (if the true probability of STR is $< 1/6$) is 0.0697. On the other hand, the probability of observing $\leq 3/10$ STR in the sample (if the true probability of STR is $> 40\%$) would be 0.3822.

7 Statistical analysis

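### The serious-toxicity list behind the 4-of-10 stopping rule misses short febrile or infected neutropenia when the patient recovers and stays on treatment; one added item closes this small gap

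*Protocol*

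**What the plan says.** Protocol 10.1 and SAP 6.2 carry the same six-item list of serious toxicities. Two items can capture neutropenia: "Drug-related grade 4 neutropenia lasting for more than seven days" and "Any other grade 3/4 drug-related event leading to early study discontinuation". No item mentions fever, sepsis or infection. The look takes place when ten patients in each group have been recruited and followed for at least four weeks, and four or more affected patients stop the trial. SAP 6.2 adds that the study stops "if the stopping rule described below is met in any of the groups".

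The dosing rules draw the line elsewhere. Table 13 in Protocol 7.2.3.1 requires a one-level reduction for grade 4 neutropenia with fever of 38.5°C or above and for "Grade 4 neutropenia with sepsis or severe infection", with no minimum duration for either. Under Protocol 7.2.3.2, once the toxicity has resolved, "patients may continue treatment at one dose level below".

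Protocol 7.2.2 takes some of these patients off treatment: "If both Day 8 and Day 15 infusions cannot be administered for any reason, the patient should discontinue the treatment", and "A maximum delay of two weeks is allowed for recovery from drug-related AEs". Both provisions allow an exception for obvious clinical benefit agreed with the sponsor.

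Protocol Table 6 gives the dose-limiting toxicities seen in phase I on this schedule. At 2.5 and 3.0 mg/m² they include "grade 3 febrile neutropenia, grade 3 anemia, grade 4 neutropenia, grade 4 thrombocytopenia and grade 4 leukopenia".

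**The concern.** A patient with, say, five days of grade 4 neutropenia and sepsis, who recovers within the limits of Protocol 7.2.2 and continues at 1.6 mg/m², meets none of the six items on account of that episode. Nor does a patient with grade 3 febrile neutropenia who continues. A patient with grade 3 fatigue does count.

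Marrow suppression is a known toxicity of the drug, and febrile or infected neutropenia is its clinically serious form. The 4-of-10 count is the only prespecified trigger for stopping and re-evaluating the dose or schedule. An event that never enters the count cannot contribute to that decision, however well the individual patient is managed.

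The duration item is a weak substitute. Protocol 1.3.5.5.2 describes the neutropenia as short-lasting. That is reassuring in general, but it also means that a requirement of more than seven days will seldom capture a complicated episode.

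**Working it through.** **1. Does the patient fall outside every item?** Take drug-related grade 4 neutropenia of seven days or less, with fever, sepsis or severe infection, in a patient who recovers and continues.

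- Neutropenia item: not met, because the duration is too short.
- Thrombocytopenia, nausea/vomiting, transaminase and fatigue items: not relevant to this episode.
- Catch-all: not met, because she does not discontinue.

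If she misses both Day 8 and Day 15, or has not recovered after a two-week delay, Protocol 7.2.2 says she should stop treatment. Reading the plan in its favour, so that stopping treatment satisfies the catch-all's wording about study discontinuation, she is then counted. The gap is therefore confined to patients who recover and continue.

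**2. The plan's own figures.** Inputs from Protocol 10.1 are n = 10, stop at X ≥ 4, and reference rates of 1/6 and 40%. With X ~ Binomial(10, p):

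- P(X ≥ 4 | p = 1/6) = 1 − (0.1615 + 0.3230 + 0.2907 + 0.1550) = 0.0697. Stated: 0.0697.
- P(X ≤ 3 | p = 0.40) = 0.0060 + 0.0403 + 0.1209 + 0.2150 = 0.3823 (unrounded 0.38228). Stated: 0.3822, the same value truncated.

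Both reproduce. They are correct for the list as written.

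**3. Illustrative effect of adding an item.** The documents give no rate of febrile or infected neutropenia at 2 mg/m². As an assumption, let the new item add 0, 1 or 2 percentage points of patients not otherwise counted, on top of a fixed rate for the existing list. Because either group can stop the study, the either-group probability is also shown as 1 − (1 − P)², taking the groups as independent with equal rates.

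| Added points (assumed) | P(stop) per group, listed rate 1/6 | P(stop) in either group, listed rate 1/6 | P(not stopping) per group, listed rate 40% |
|---|---|---|---|
| 0 | 0.0697 | 0.1346 | 0.3823 |
| 1 | 0.0835 | 0.1599 | 0.3575 |
| 2 | 0.0986 | 0.1874 | 0.3335 |

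**4. How often would such a patient appear?** Among the 20 patients at the two looks, the chance of at least one is 1 − 0.99²⁰ = 0.18 at 1 point and 1 − 0.98²⁰ = 0.33 at 2 points. This describes how often the item would be used. It is not the chance that it changes the decision, which is given by the differences in the table.

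**The case against.** The best defence is that the event is rare at the trial dose. On this schedule the only dose-limiting toxicity listed at 2 mg/m² is a grade 4 lipase increase; febrile neutropenia is listed only at the two levels judged too toxic. Protocol 1.3.5.1 says hematological events were mostly mild to moderate and without fever or infection. Protocol 1.3.5.5.2 reports a low rate of grade 3/4 neutropenia at 2 mg/m², and Protocol 1.4 reports that no doses were skipped for it. All of this stands, and it is why the point is small. It does not rule the event out, since an episode in the rest week need not cause a skipped dose.

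Second, the effect on decisions is slight. With the assumed 1 or 2 points, the stopping decision changes in 1.4% or 2.9% of groups at a listed rate of 1/6, and in 2.5% or 4.9% at 40%. At 2 points, false stopping rises by about 41% in relative terms (0.0986/0.0697), while failure to stop falls by about 13% (0.3335/0.3823). That trade-off is real and has to be accepted knowingly.

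Third, stopping criteria need not mirror dose-reduction criteria, and other events are also uncounted when treatment continues. Grade 4 lipase and grade 4 troponin increases, both seen at 2 mg/m², are examples. The principle is sound, but those omissions do not justify this one. The proposed item also goes beyond Table 13 by including grade 3 febrile neutropenia; the support for that is the phase I dose-limiting toxicity on the same schedule.

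Fourth, dose reduction, 24-hour SAE reporting (Protocol 9.2.2) and optional unscheduled safety analyses (SAP 6.2) give partial cover. They do protect patients, but none of them puts the event into the 4-of-10 count.

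**Conclusion.** The concern holds as a modest, low-cost improvement. The gap follows directly from the text: short febrile or infected neutropenia, with recovery and continued treatment, is not a serious toxicity for the stopping rule, although grade 4 neutropenia with these complications requires a dose reduction under the protocol's own table.

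Its size cannot be estimated from the documents, and the phase I evidence suggests it is small at 2 mg/m². The 1- and 2-point figures are assumptions, and the either-group figures further assume independent groups with equal rates. The rule is not wrong on its own terms: its stated probabilities are correct, and the seven-day threshold for uncomplicated grade 4 neutropenia is not in dispute.

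**What to change.** Add one item to the lists in Protocol 10.1 and SAP 6.2: *Drug-related grade 3/4 febrile neutropenia, or drug-related grade 4 neutropenia with fever of 38.5°C or above, sepsis or severe infection, of any duration.* Keep the existing item of more than seven days for uncomplicated grade 4 neutropenia, and keep the boundary of 4 or more of 10. Apply the same list to SAP Table 12.2.2.1 and Listing 12.2.2.1. No other count or threshold is needed.

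The drafting cost is one line in each document; blood counts and adverse events are already collected. The statistical cost is a somewhat higher chance of stopping at an acceptable dose: at a listed rate of 1/6 and 2 added points, 0.0986 instead of 0.0697 per group and 0.1874 instead of 0.1346 for either group. At 1 added point the figures are 0.0835 and 0.1599.
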